OBSERVATIONAL STUDY

Clinical and Economic Outcomes of hs-cTns for diagnosis of NSTEMI in Patients With Chest Pain in EDs in Italy-An Observational Study - TROCAR 2017

No Profit Study: TROCAR 2017

Promoter

National Institute of Health - Istituto Superiore di Sanità (ISS)
National Centre for Health Technology Assessment - Centro Nazionale per l'Health
Technology Assessment (HTA)
[name]
[name]

Version 13_April_2017

SUMMARY

This multicenter observational study is a clinical, organizational and economic evaluation of the different quantitative assays of high-sensitivity cardiac troponin in patients with suspected acute myocardial infarction and non-ST-elevation ECG (NSTEMI) at admission at 12 Italian Emergency Departments.

This document provides a synopsis of the Study Protocol (original in Italian)

SYNOPSIS

Title	Clinical and Economic Outcomes of hs-cTns for diagnosis of NSTEMI in Patients With Chest Pain in EDs in Italy-An Observational Study TROCAR 2017
Promoter	National Institute of Health National Health Technology Assessment Centre
Type of study	No profit with in vitro diagnostic medical devices routinely employed in clinical practice
Clinical phase	Post marketing
Background	Myocardial infarction is one of the leading causes of death and disability worldwide. In addition to standard diagnostic methods, it has been shown that high-sensitivity cardiac troponin assays allow greater sensitivity in the diagnosis of myocardial infarction and assume a central role for both exclusion ("rule out") and confirmation ("rule in") of acute myocardial infarction, while allowing to reduce the time interval between Emergency Department admission and presumptive diagnosis.
	Considering the relevance of this topic, we propose to conduct an observational study in real world clinical practice settings at Emergency Departments, aiming to evaluate clinical and economic aspects deriving from the use of the different quantitative assays of high-sensitivity cardiac troponin currently available in patients with suspected acute myocardial infarction and non-ST-elevation ECG (No ST elevation myocardial infarction - NSTEMI) at admission, including time of diagnosis and number of laboratory and imaging tests performed.
Study design	Observational
Objective	Clinical, organizational and economic evaluation of the different quantitative assays of high-sensitivity cardiac troponin in patients with suspected acute myocardial infarction and non-ST-elevation ECG (NSTEMI) at admission at the Emergency Department

Primary Endpoint	Time to diagnosis at the Emergency Department
Secondary Endpoints	% rule in patients (NSTEMI diagnosis)
	% rule out patients (exclusion of NSTEMI)
	% patients dead 30 days after Emergency Department admission
	% patients with myocardial infarction 30 days after Emergency
	Department admission
	% patients with major adverse events 30 days after ED
	admission
Pharmacoeconomic	Number and cost of laboratory and imaging tests performed at
endpoint	the Emergency Department
Evaluation of	Outcome measures: time of diagnosis, death or myocardial
effectiveness	infarction 30 days after Emergency Department admission.
	Sensitivity and Negative Predictive Value of myocardial Infarction
	("rule out") with different quantitative assays of high-sensitivity
	cardiac troponin, according to the standard operating protocols
	of the participating Centers.
	Sensitivity and Negative Predictive Value will be evaluated in
	relation to:
	a) limit of detection of the used assay
	b) 99th percentile of the reference healthy population
	Evaluation of 30-day prognosis
	Evaluation of costs of any further examinations after the first
Safety evaluation	N.A. (already provided in the Hospital)
Expected number of	
patients	300 patients for each centre
Type of patients	Patients with suspected acute myocardial infarction and non-ST-
l ypo or pationto	elevation ECG (NSTEMI) at admission at the Emergency
	Department
Type and number of	12 Emergency Departments
centres	
Enrollment	Consecutive
Number of examinations	Patients will be examined at enrollment in the Emergency
	Departments, and after 30-days
Inclusion and exclusion	Inclusion criteria
criteria	
	both sexes
	≥18 years old
	Patients with chest pain
	At least one high-sensitivity cardiac troponin test
	performed
	Written informed consent

	Exclusion criteria
	 Refusal to provide informed consent Elevation of ST segment in the ECG Pregnancy or breastfeeding Any other clinical conditions not compatible with participation at the study
Used in-vitro medical device	Different quantitative assays of high-sensitivity cardiac troponin currently available and used in the Emergency Department
Length of study	January 2018 - July 2018

References

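### Does leaving the scored troponin sample unstated make the planned sensitivity and NPV depend on how many samples each centre drew?

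*Protocol*

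**What the plan says.** Under Evaluation of effectiveness, the protocol synopsis plans "Sensitivity and Negative Predictive Value of myocardial Infarction" for rule-out, with the different assays of high-sensitivity "cardiac troponin, according to the standard operating protocols" of the participating centres. Both measures are to be evaluated at two thresholds: "a) limit of detection of the used assay" and "b) 99th percentile of the reference healthy population". The same section names as outcome measures the time of diagnosis and death or myocardial "infarction 30 days after Emergency Department admission", and it adds a line on cost, "Evaluation of costs of any further examinations after the first".

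Inclusion requires "At least one high-sensitivity cardiac troponin test"; no number or timing of samples is fixed. The objective is a clinical, organizational and "economic evaluation of the different quantitative assays of high-sensitivity cardiac troponin".

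The SAP covers the sample size for time to diagnosis, descriptive summaries and a logistic regression for 30-day prognosis. It has no paragraph on sensitivity or NPV. The protocol's Summary says that the published document is a synopsis of a protocol written in Italian.

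**The concern.** A threshold does not define a test result until one knows which measurement is compared with it: the first, a timed later one, the highest, or any. The synopsis leaves this to local practice, and patients may have one sample or several. The titles in the reference list suggest no common default, since they cover presentation, one-hour, two-hour, presentation-plus-three-hour and serial-change approaches.

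If each patient were scored on whatever the centre drew, an assay used where repeat sampling is common could show higher sensitivity at the 99th percentile than an equally good assay used where it is not. A difference in sampling would then look like a difference between assays, in a study whose objective is to evaluate the assays. The reference is also open: MI at 30 days is mentioned nearby, but nothing ties it to the accuracy analysis.

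**Working it through.** **The plan's own figure.** The only computed figure in the documents is the sample size: (1.96 × 5 / 0.5)² = 384.2, given as 384, and 384 × 1.30 = 499.2, rounded to 500 per centre. It reproduces, but it concerns time to diagnosis. No accuracy figure is given, so every accuracy input below is an assumption.

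**Direction.** Fix the patients and the MI reference. The MI patients who are positive on at least one of k samples include all who are positive on the first. Sensitivity under that rule therefore cannot fall as k rises, though it may stay equal. NPV has no fixed direction, because extra samples also create false positives. Take 30 MIs with 3 missed and 230 of 270 non-MI patients negative: NPV = 230/233 = 98.7%. If later samples catch no missed MI and leave 195 non-MI patients negative, NPV = 195/198 = 98.5%.

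**Size, first model.** Let s be first-sample sensitivity and q the share of still-negative MIs picked up by each further sample. Sensitivity after m further samples is 1 − (1 − s)(1 − q)^m.
- s = 80%, q = 50%: 80.0%, 90.0% and 95.0% with one, two and three samples.
- s = 80%, two samples: 85.0% if q = 25%, 95.0% if q = 75%.
- If only half of the first-sample negatives are resampled, the 10-point gain at q = 50% becomes 5 points.
- At the LoD, with s = 98% and q = 50%, sensitivity goes from 98% to 99% with two samples.

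**Size, second model.** Sensitivity is 1 − P(all k samples negative), with a beta-binomial for within-patient correlation.

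| Per-sample sensitivity | Correlation | 1 sample | 2 samples | 3 samples |
|---|---|---|---|---|
| 80% | 0 | 80.0% | 96.0% | 99.2% |
| 80% | 0.5 | 80.0% | 88.0% | 91.2% |
| 80% | 0.8 | 80.0% | 83.2% | 84.7% |
| 90% | 0 | 90.0% | 99.0% | 99.9% |
| 90% | 0.5 | 90.0% | 94.5% | 96.2% |
| 90% | 0.8 | 90.0% | 91.8% | 92.6% |

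From one to three samples the rise is between 2.6 and 19.2 points.

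**Against sampling error.** Assume 10% MI.
- Whole study, 12 × 300 patients: 288/360 = 80%, exact 95% CI 75.5% to 84.0%. With 12 × 500: 480/600, CI 76.6% to 83.1%. A 10-point shift lies outside both. The 83.2% of the correlation-0.8 case lies inside the first and marginally outside the second.
- One centre of 300: 24/30, CI 61.4% to 92.3%. A 10-point shift lies inside.
- The worry, however, is about assays compared with each other. With three centres per assay (an assumed allocation) there are 90 MIs per assay at 300 per centre. The 95% margin on 80% against 90% is 1.96 × √(0.16/90 + 0.09/90) = 10.3 points. At 500 per centre (150 MIs per assay) it is 8.0 points. A 10-point artefact is thus about the size of the noise in that comparison.

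**Would fixing the first sample remove the dependence?** Not fully, if the reference includes MI diagnosed at the index visit. Take 30 true MIs, 24 positive on the first sample, with q = 50%. Suppose an MI is recognised if a drawn sample is positive, and half of the rest are recognised by day 30.
- One sample: 24/(24 + 3) = 88.9%.
- Two samples: 24/(27 + 1.5) = 84.2%.
- Three samples: 24/(28.5 + 0.75) = 82.1%.

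The true first-sample value is 80%. The figure still varies with the number of samples, now through the reference.

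**The case for a change.** The best case for a change is this. The synopsis promises accuracy at two named thresholds, and a result from a whole local pathway is not accuracy at a threshold. The direction for sensitivity is a matter of set inclusion and needs no model. A short paragraph naming the scored sample and the reference would cost little, and the pathway result could still be reported beside it.

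The logic about direction stands, and so does the fact that neither supplied document names the sample or the reference. The rest is weaker. Scoring on any sample is one reading; the mention of local operating protocols may simply describe how the assays are used. The cost line on further examinations need not mean repeat troponin, since the economic endpoint covers laboratory and imaging tests generally. Only the inclusion criterion shows directly that sample numbers may vary. The SAP's sentence on comparing centres closes the paragraph on 30-day prognosis and is not clearly about accuracy. The documents do not promise an assay property independent of the pathway, nor a formal accuracy test between assays.

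**Conclusion.** No change to the plan follows. The gap is real but is one of missing detail: the public synopsis and SAP leave the scored sample and the MI reference unwritten, and the full Italian protocol may define both. No rule that the documents state is shown to give a wrong result. The possible distortion depends on a scoring rule that they do not contain. If that rule were used, sensitivity from one to three samples could rise by roughly 3 to 19 points under assumed per-sample sensitivities of 80% or 90% and correlations from 0 to 0.8, with little effect at the LoD and no fixed direction for NPV.

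Accuracy under each centre's own protocol is a fair target for an observational study of routine practice. An analyst computing these measures has to choose a sample and a reference in any case, and can state the choice with the results. Prescribing the first sample would not by itself make the figure independent of sampling. Time to diagnosis, the listed secondary endpoints and the cost endpoint are untouched.

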## STATISTICAL ANALYSIS

The definition of the sample size was made to estimate, with a confidence interval of 95% and with a precision of 30 minutes, the time of diagnosis at the Emergency Department that, from literature data, is of 5 hours on average, with a standard deviation of 5 hours.

Considering these assumptions, the number of subjects to be enrolled per center would be equal to 384. This number was increased by 30% and was therefore raised to 500 subjects per center to minimize the effect of "drop out" or patients with incomplete data.

Central tendency and dispersion measures will be used to describe the quantitative variables; absolute and relative frequencies will be used to report the qualitative ones.

To identify correlates of prognosis after 30 days, a multivariate logistic regression model will be used with variables collected during the enrolment categorized as dependent variables. The multivariate model will be developed using backward elimination with confidence intervals at the 95% level. Results will be compared also between centers.

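### Does answering drop-out and incomplete data only with over-enrolment leave the primary endpoint, time to diagnosis, open to a bias that requires a change to the SAP?

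*SAP*

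**What the plan says.** The protocol synopsis names one primary endpoint, "Time to diagnosis at the Emergency Department", and does not define when the clock starts or stops. The Statistical Analysis section of the SAP sizes each centre to estimate this time, which it says "is of 5 hours on average, with a standard deviation of 5 hours", with a 95% confidence interval and a precision of 30 minutes. The result is 384 per centre. The SAP then adds: "This number was increased by 30% and was therefore raised to 500 subjects per center to minimize the effect of" drop-out "or patients with incomplete data".

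On analysis, the relevant sentence is "Central tendency and dispersion measures will be used to describe the quantitative variables". The supplied text has no rule for a missing diagnosis time: no censoring, imputation or sensitivity analysis. The last paragraph concerns a different outcome ("To identify correlates of prognosis after 30 days, a multivariate logistic regression model will be used") and closes with "Results will be compared also between centers", which may refer only to that model.

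Two further features of the synopsis matter. Patients are seen in the Emergency Department and again at 30 days, so there is a later point at which they can be lost. The document also describes itself as a synopsis of a fuller Italian protocol.

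**The concern.** Over-enrolment addresses the variance of an estimate, not its bias. If patients without a diagnosis time differ systematically from the rest, 500 patients give a narrower interval around the same wrong value.

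Time to diagnosis is a waiting time, which makes the worry natural. A patient whose diagnosis takes longer has more opportunity to walk out or be transferred first. If those patients drop out of the summary, the mean and median of the remainder are too short. Describing a variable by central tendency and dispersion, with no missing-data rule, most readily means using the patients with a recorded time.

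At stake is whether the reported time is right to within the 30 minutes for which the study was sized. If time to diagnosis were also compared between centres, unequal loss before diagnosis could produce a difference that is not real.

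**Working it through.** **The plan's own figures.** Inputs from the SAP: SD 5 h, half-width 0.5 h, 95% confidence.

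- n = (1.96 × 5 / 0.5)² = 384.2, stated as 384.
- 384 × 1.30 = 499.2, stated as 500.
- Half-width is 1.96 × 5/√n h: 30.0 min at 384 and 26.3 min at 500. At the synopsis's figure ("300 patients for each centre") it is 33.9 min. The difference between 300 and 500 is a separate matter and does not affect the bias.

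**What drives the bias.** Let f be the share with no diagnosis time. The true mean is (1 − f) × mean(observed) + f × mean(lost), so

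error of complete-case mean = f × [mean(observed) − mean(lost)].

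Sample size does not appear. For the error to reach −30 min, the lost patients' eventual times must exceed the observed ones on average by 0.5/f hours: 25 h at 2% loss, 10 h at 5%, 5 h at 10%.

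**Size under departure unrelated to diagnosis time.** Assumptions, none in the documents: f from 2% to 10%, a constant leaving rate, and exponential or lognormal times with mean and SD 5 h. For the exponential, the complete-case mean is 5(1 − f) h.

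| Assumed loss | Error in mean (min) | Error in median (min) |
|---|---|---|
| 2% | −6 | −3 to −4 |
| 5% | −14 to −15 | −7 to −10 |
| 10% | −28 to −30 | −13 to −21 |

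The 10% row implies that leavers would have been diagnosed at about 9.1 to 9.5 h on average, against about 4.5 h in those observed. Check for the exponential: 0.10 × (4.5 − 9.5) = −0.5 h = −30 min.

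**Same 10% loss, other mechanisms.**

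| Who is lost | Error in mean (min) |
|---|---|
| Shortest 10% of times | +28 to +32 |
| Completely at random, or lost only to 30-day follow-up | 0 |
| Half unrelated to time, half by independent departure | −14 to −16 |
| Longest 10% of times | about −76 |

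The documents do not say which row applies, so neither size nor sign can be established.

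**Would censoring at departure repair it?** Kaplan-Meier is essentially exact when departure is independent of diagnosis time, because that is its own assumption. With departure and diagnosis times linked by a Gaussian copula (10% loss, one million draws), the errors in minutes are:

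| Correlation | Complete-case mean | 24 h restricted mean (Kaplan-Meier) |
|---|---|---|
| −0.5 | about −52 | −18 to −19 |
| +0.3 | −13 to −17 | about +9 |
| +0.5 | −2 to −9 | about +15 |

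Censoring is better in the first two rows and worse in the third, where those who leave early would have had short times.

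**The case for a change.** The strongest case for acting is that the omission is certain even if its size is not. The 30% allowance inflates a number derived solely for time to diagnosis and covers incomplete data as well as drop-out. It is therefore hard to read it as concerning only the 30-day visit, and 384/500 leaves room for about 23% loss. If 10% of patients did leave undiagnosed under independent departure, coverage of a nominal 95% interval would fall to about 53–54% with 300 enrolled and 35–36% with 500. A few sentences in the SAP would cost little, and with no missing times a censored analysis reduces to the ordinary summary.

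It stands that over-enrolment cannot remove bias and that the supplied text has no missing-time rule. The step to a material defect does not stand:

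- The 30% is a general allowance, not a forecast of patients leaving before diagnosis.
- At 2% loss the same mechanism gives 6 minutes, a fifth of the planned precision, with coverage still 90–93%.
- Enrolment requires written consent and at least one troponin test. Some who leave very early may never be enrolled, and censoring could not recover them.
- A complete-case mean is inferred. The SAP names no estimator, and a median shifts less.
- Censoring needs departure times for undiagnosed patients, which the documents do not show are collected, and it estimates the time that would apply if nobody left. Statisticians could reasonably prefer a plain summary with counts.

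**Conclusion.** No change to the plan follows. The arithmetic behind the concern is correct, and 28 to 30 minutes at 10% loss would be as large as the planned precision. But that figure rests on an assumed loss rate, an assumed departure mechanism, assumed distribution shapes and an inferred estimator. Under equally admissible assumptions at the same loss, the error runs from about 30 minutes too long to about 76 minutes too short, and it is nil if times are missing at random or if drop-out means loss to 30-day follow-up. No statement in either document points to appreciable departure without a diagnosis among enrolled patients.

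What is left is a detail that the available text does not spell out, in a descriptive observational study whose fuller Italian protocol is not to hand. Analysts ordinarily fill it by reporting, per centre, how many diagnosis times are missing and why, and by reading the summary accordingly. A censored analysis is a reasonable sensitivity check if those counts prove more than trivial and departure times exist. It is not clearly better as the primary summary. The conclusion would differ if the study's own data, or the full protocol, showed that a substantial share of enrolled patients left before diagnosis.

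### The protocol synopsis expects 300 patients per centre but the SAP sets 500; at 300, the SAP's ±30-minute per-centre precision is not met

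*SAP*

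**What the plan says.** The SAP (Statistical Analysis, first two paragraphs) sizes the study on time to diagnosis, which the protocol synopsis names as the primary endpoint. The aim is to estimate the mean "with a confidence interval of 95% and with a precision of 30 minutes", assuming a mean of 5 hours and a standard deviation of 5 hours. From this the SAP concludes that "the number of subjects to be enrolled per center would be equal to 384". It adds 30% for drop-out and incomplete data, so the number "was therefore raised to 500 subjects per center".

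The protocol synopsis, in the row for the expected number of patients, gives "300 patients for each centre". The row for type and number of centres gives "12 Emergency Departments".

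Both figures are explicitly per centre, and neither is marked as superseded. The protocol's Summary says that the public document is a synopsis of an Italian original. The absence of reconciling text can therefore be shown only for the synopsis and the SAP.

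**The concern.** The planned sample size is a basic design parameter, and here it has two values that differ by 200 per centre. A final total near 3,600 would be full recruitment under the synopsis and a 40% shortfall under the SAP, and the documents do not say which reading applies.

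The disagreement also affects the only justification the SAP gives for its size. That justification is a precision target for each centre. The synopsis figure lies below the SAP's final 500 and also below the 384 that the SAP needs before any allowance for loss. If the synopsis figure is the operative one, the stated per-centre precision on the primary endpoint cannot be met under the SAP's own assumptions.

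**Working it through.** **Inputs.** From the SAP: 95% confidence (two-sided, z = 1.96), half-width 30 min, SD 5 h = 300 min, 30% increase, 384 and 500 per centre. From the protocol synopsis: 300 per centre, 12 centres. The assumed mean of 5 h does not enter the formula.

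**Reproducing the SAP's figures.**

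- n = (z × SD / half-width)² = (1.96 × 300 / 30)² = 384.2, against the stated 384.
- 384 × 1.30 = 499.2, against the stated 500.

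Both reproduce, so the SAP is consistent with itself. A one-sided reading (z = 1.645) gives 271, which matches neither 384 nor 300.

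**Per-centre precision at each figure.** Half-width = 1.96 × 300 / √n:

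| Evaluable patients per centre | 95% half-width (min) |
|---|---|
| 500 (SAP target, no loss) | ±26.3 |
| 385 | ±29.97 |
| 384 (SAP requirement) | ±30.0 |
| 300 (synopsis, complete data) | ±33.9 |
| 231 (300 / 1.3) | ±38.7 |
| 210 (300 × 0.7) | ±40.6 |

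- At 300 with complete data, 33.9 / 30 = 1.13, so the interval is 13% wider than stated.
- The last two rows are illustrative. The SAP states no loss rate, and neither document applies a loss allowance to 300. Reversing the ×1.30 factor implies a loss of 1 − 1/1.3 = 23.1%; a literal 30% loss leaves 210.
- SD at which 300 complete cases would give ±30 min: 30 × √300 / 1.96 = 265 min, against the SAP's 300.
- Loss tolerated if 500 are enrolled: 1 − 385/500 = 23%.

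**Totals.** 12 × 300 = 3,600; 12 × 500 = 6,000; difference 2,400.

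**Pooled estimate at the lower total.** 1.96 × 300 / √3,600 = ±9.8 min, ignoring clustering by centre.

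**The case against.** The strongest case on the other side accepts the discrepancy and disputes its weight.

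- **Size of the effect.** The study is observational and descriptive on this endpoint. No test, power statement or decision rule depends on 30 minutes, and with complete data the shortfall is about 4 minutes. The SD is a literature value given in whole hours. At 4.5 h (270 min), 300 patients give 1.96 × 270 / √300 = ±30.6 min, so the gap is within the uncertainty of that input. This stands as a limit on the precision consequence. It does not settle which enrolment figure applies.
- **Expected number or target.** The synopsis speaks of an expected number, which might be a forecast, a minimum or an evaluable count. No text says so. As an evaluable count out of 500 it would imply 40% loss, well beyond the 23% that the SAP's allowance covers. On any of these readings 300 is still below 384.
- **Unseen text and order of the documents.** The Italian original may reconcile the figures. The SAP text available carries no date, so whether one document replaced the other cannot be seen. Both limits are real, but the two public documents would still disagree and need correcting.
- **Between-centre comparison.** The SAP's sentence "Results will be compared also between centers" closes the paragraph on the 30-day prognosis model, so it may not refer to time to diagnosis. That is fair. The point does not need that sentence, because the sample-size paragraph itself sets the target per centre.
- **Loss scenarios.** The ±38.7 and ±40.6 min figures are hypothetical, so the complete-data ±33.9 min should lead.

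**Conclusion.** The concern holds. As written, one figure that the study relies on is wrong: either the synopsis's 300 per centre, or the SAP's 500 together with its ±30-minute precision. The certain consequence is an ambiguity of 2,400 patients in planned enrolment. The precision consequence is conditional on 300 governing, and it is modest: ±33.9 instead of ±30 minutes per centre with complete data, more with losses, and no material effect on an estimate pooled over all centres. These figures rest on the SAP's SD of 300 minutes, a two-sided 95% normal interval for a single mean, and the synopsis and SAP as published. The correction should be made because it concerns the stated sample size, even though the loss of precision is small.

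**What to change.** State one per-centre target and the matching total in both documents.

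- **If the target is 300 (3,600 in total):** in the SAP, replace the 500 and the ±30-minute statement with a per-centre precision of about ±34 minutes with complete data. Put the assumed loss rate beside any post-loss figure (about ±39 minutes at 23% loss, about ±41 minutes at 30%).
- **If 500 is already the operative target (6,000 in total):** correct the synopsis to 500 per centre and leave the SAP's calculation as it is.

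Either route changes wording only. The first accepts a slightly less favourable stated precision and adds no patients; the second changes one figure in the synopsis. Raising recruitment to 500 where 300 was the real plan would mean 2,400 more patients, and that is not proposed.
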